## **5.7. Concomitant Treatment(s)**

Concomitant treatment considered necessary for the participant's well-being may be given at the discretion of the treating physician.

Prophylactic antipyretics and other pain medications to prevent symptoms associated with investigational vaccine administration are not permitted.

All concomitant treatments, blood products, as well as non-drug interventions received by participants from screening until the end of study visit will be recorded on the Case Report Form (CRF).

#### **5.7.1. Prohibited Concomitant Vaccines**

No vaccines (licensed or investigational) other than study vaccine, influenza and pneumococcal vaccines should be given during the study within 30 days prior to or after dosing. Other vaccines may be administered only if medically necessary (eg, tetanus post exposure prophylaxis).

For participants who receive tremelimumab, live attenuated vaccines should not be administered within 30 days prior to or after dosing with tremelimumab. The administration of inactivated vaccines is allowed.

#### **5.7.2. Other Anti-tumor/Anti-cancer or Experimental Drugs**

No additional anti-tumor treatment will be permitted while participants are receiving study treatment. Additionally, the concurrent use of vitamins or herbal supplements for an anticancer treatment is not permitted.

Participants currently being treated with a GnRH agonist or antagonist may continue treatment while participating in this study as long as the GnRH agonist treatment has been well tolerated for at least three months prior to study entry.

#### **5.7.3. Participants on beta blockers**

Per the TDS-IM Investigator's Brochure (28-Jun-2019), two cases of syncope have been reported in association with the device in a total of over 800 subjects receiving up to 5 administrations. Caution should be undertaken during injections in participant taking beta blockers. Strong consideration should be given to placing the participant in prone position depending on the participant's medical condition.

#### **5.7.4. Supportive Care**

Palliative and supportive care for disease related symptoms may be administered at the investigator's discretion and according to any available American Society of Clinical Oncology (ASCO) guidelines.

Participants currently being treated with denosumab or bisphosphonates (eg, zoledronate) for bone disease may continue treatment while participating in this study. However, initiation of treatment with these types of compounds should be avoided while participating in the study.

#### **5.7.5. Anti-Diarrhea and Anti-Emetic Therapy**

Primary prophylaxis of diarrhea, nausea and vomiting is not permitted prior to the first dose of adenovirus, tremelimumab and/or PF-06801591. Primary prophylaxis on subsequent dosing days is at the investigator's discretion. The choice of the prophylactic drug is up to the investigator with sponsor approval and assuming the drug is not included in the **Concomitant Treatment(s)** section, as well as the duration of treatment assuming there is no known or expected drug-drug interaction. If so, then it must be approved by the sponsor.

### **5.7.6. Anti-inflammatory Therapy**

Anti-inflammatory or narcotic analgesic may be offered as needed assuming there is no known or expected drug-drug interaction and assuming the drug is not included in the [Concomitant Treatment\(s\)](#) section.

### **5.7.7. Therapy for Treatment of Pyrexia and Flu-like Symptoms**

Primary prophylaxis of fever or flu-like symptoms is not permitted prior to dosing of adenovirus. Following receipt of adenovirus, medications used to treat fever or flu-like symptoms (eg, acetaminophen, ibuprofen) should be administered at the first sign of either event.

### **5.7.8. Corticosteroids**

Chronic, systemic corticosteroid use for palliative or supportive purpose is not permitted. The short term use of corticosteroids for medically indicated conditions is allowed and should be discussed with the sponsor. Topical, nasal and inhaled corticosteroids are allowed.

### **5.7.9. Surgery**

Caution is advised on theoretical grounds for any surgical procedures during the study. The appropriate interval of time between surgery and administration of the PrCa VBIR components or combination agents required to minimize the risk of impaired wound healing and bleeding has not been determined. Stopping all components of PrCa VBIR, PF-06801591 is recommended at least 7 days prior to surgery. Postoperatively, the decision to reinitiate treatment should be based on a clinical assessment of satisfactory wound healing and recovery from surgery.

## **6. STUDY PROCEDURES**

### **6.1. Screening**

For screening procedures see [Schedule of Activities](#) and [ASSESSMENTS](#) section.

### **6.2. Study Period**

For treatment period and maintenance treatment period procedures, see [Schedule of Activities](#) and [ASSESSMENTS](#) section.

### **6.3. Follow-up Period**

Patients who have permanently discontinued treatment with the study drugs will complete the assessments required for the End of Treatment visit and then enter the follow-up period which includes 6 months of additional evaluations. For follow-up procedures see [Schedule of Activities](#) and [ASSESSMENTS](#) section.

### **6.4. Patient Withdrawal**

Participant withdrawal may include either: (a) withdrawal from treatment with continued follow up, or (b) withdrawal from treatment and no further follow up.

#### **6.4.1. Withdrawal from Treatment**

Participants may withdraw from treatment at any time at their own request, or they may be withdrawn from treatment at the discretion of the Investigator or Sponsor for the following reasons: (a) safety, (b) lack of efficacy, (c) behavioral reasons, or (d) the inability of the participant to comply with the protocol-required schedule of study visits or procedures at a given study site. Reasons for withdrawal of study treatment may include:

- Objective disease progression by irRECIST (see [Appendix 4](#)). Disease progression will be confirmed with two consecutive timepoints at least 4 weeks (or at least 6 weeks for progressing disease on bone scan) apart in the absence of rapid clinical deterioration;
- Global deterioration of health status requiring discontinuation;
- Unacceptable toxicity, including treatment-related DLT;
- Significant protocol violation;
- Lost to follow-up (defined as: If a participant repeatedly fails to return for scheduled visits and repeated attempts to contact the patient have been unsuccessful);
- Participant refused further treatment;
- Study terminated by sponsor;
- Death.

#### **6.4.2. Withdrawal from Study**

Reasons for withdrawal from study follow-up may include:

- Completed study follow-up;
- Study terminated by sponsor;
- Lost to follow-up (defined as: If a participant repeatedly fails to return for scheduled visits and repeated attempts to contact the patient have been unsuccessful);
- Refused further follow-up;
- Death.

If a participant does not return for a scheduled visit, every effort should be made to contact the participant. All attempts to contact the participant and information received during contact attempts should be documented in the participant's medical record. In any circumstance, every effort should be made to document participant outcome, if possible. The investigator should request that the participant return for a final visit, if applicable, and follow-up with the participant regarding any unresolved AEs.

If the participant refuses further visits, no further study specific evaluations should be performed, and no additional data should be collected. The sponsor may retain and continue to use any data collected before such withdrawal of consent. Publicly available information may be used to determine follow up information as appropriately directed in accordance with local law.

## 7. ASSESSMENTS

Every effort should be made to ensure that the protocol-required tests and procedures are completed as described. However, it is anticipated that from time to time there may be circumstances, outside of the control of the investigator, which may make it unfeasible to perform the test. In these cases the investigator will take all steps necessary to ensure the safety and well-being of the participant. When a protocol-required test cannot be performed, the investigator will document the reason for this and any corrective and preventive actions that he or she has taken to ensure that normal processes are adhered to as soon as possible. The study team will be informed of these incidents in a timely fashion.

### 7.1. Safety Assessments

Safety assessments will include collection of adverse events (AEs), serious adverse events (SAEs), vital signs and physical examination, electrocardiogram (ECG (12 lead)), laboratory assessments, and verification of concomitant treatments.

#### 7.1.1. Adverse Events

Assessment of adverse events will include the type, incidence, severity (graded by the NCI CTCAE version 4.03) timing, seriousness, and relatedness.

Adverse events that occur during the study will be recorded on the adverse events CRF page.

#### 7.1.2. Laboratory Safety Assessment

Hematology, blood chemistry and coagulation will be drawn at the time points described in the [Schedule of Activities](#) and analyzed at local laboratories.

Hematology	Chemistry	Coagulation	Urinalysis
Hemoglobin	ALT	PT or INR	Urine dipstick for urine protein: If positive collect 24-hr and microscopic (Reflex Testing)
Platelets	AST	PTT	
WBC	Alk Phos		
Absolute Neutrophils	Sodium		
Absolute Lymphocytes	Potassium		
Absolute Monocytes	Magnesium		Urine dipstick for urine blood: If positive collect a microscopic (Reflex Testing)
Absolute Eosinophils	Chloride		
Absolute Basophils	Total Calcium		
	Total Bilirubin 		
	BUN or Urea		
	Creatinine		
	Uric Acid		
	Glucose (non-fasted)		
	Albumin		

Hematology	Chemistry	Coagulation	Urinalysis
	Phosphorous or Phosphate		
	Lactate dehydrogenase		
	Lipase		
	Amylase		
	Bicarbonate or carbon dioxide		
	Total protein		
	TSH (if abnormal, reflex free T4 and free T3 tests) 		

1. For Hy's law potential cases, in addition to repeating AST and ALT, laboratory tests should include albumin, creatine kinase, total bilirubin, direct and indirect bilirubin, gamma-glutamyl transferase, prothrombin time (PT)/INR, alkaline phosphatase, total bile acids and acetaminophen drug and/or protein adduct levels.
2. For participants in Cohorts 6A through 9A and Cohorts 3B and 5B.

### 7.1.3. Vital Signs, Physical Examination and Skin Assessment

Participants will have a physical examination to include weight, vital signs, assessment of ECOG performance status and height; height will be measured at screening only.

A complete physical examination (PE) will be performed at Screening and at the End of Treatment visit for each participant and will include an assessment of all body systems (genitourinary examination is optional). A neurologic examination must be conducted at Screening to look for potential signs suggestive of autoimmune disorders. Findings of all physical examinations should be recorded in the source documents, and any change from baseline considered by the investigator to be clinically significant should be recorded as an adverse event in the CRF.

Abbreviated PEs should be performed as appropriate per the [Schedule of Activities \(SOA\)](#), and on an as needed basis for assessment of adverse events. Abbreviated exams should be targeted to specific symptoms or complaints and be consistent with local standard of care. However, a neurologic examination must be performed during each exam conducted during Cycle 1.

Weight and body surface area (BSA) do not need to be performed at each visit; however participants should be monitored throughout the study for significant weight change.

Vital signs will include measurements of blood pressure and temperature (oral, temporal, tympanic or axillary). On dosing days, vital signs should be measured prior to administration of any of the study treatments. Sitting blood pressure (BP) will be measured with the participant's arm supported at the level of the heart and recorded to the nearest mmHg sufficient. The same arm (preferably the dominant arm) should preferably be used throughout the trial. A blood pressure cuff, which has been properly sized and calibrated, should be used to measure blood pressure. The use of automated devices for measuring BP is acceptable.

Assessment of the skin and subcutaneous tissue thickness at the eligible administration sites will be performed at screening as described in the TDS-IM Instructions for Use. The assessment procedure does not need to be repeated during the course of the study unless the participant experiences a greater than 10% change in body mass relative to screening.

#### **7.1.4. (12-Lead) ECG**

Electrocardiogram (ECG): Triplicate 12-lead (with a 10-second rhythm strip) tracing will be used for all ECGs. It is preferable that the machine used has a capacity to calculate the standard intervals automatically. At each time point (see the [Schedule of Activities](#)), three consecutive ECGs will be performed at approximately 2 minutes apart to determine the mean QTcF interval. If the mean QTcF is prolonged (value of >500 msec), the ECGs should be re-evaluated by a qualified person at the institution for confirmation. If manual reading verifies a QTcF of >500 msec, immediate correction for reversible causes (including electrolyte abnormalities, hypoxia and concomitant medications for drugs with the potential to prolong the QTcF interval) should be performed. In addition, repeat ECGs should be immediately performed hourly for at least 3 hours until the QTcF interval falls below 500 msec. If QTcF interval reverts to less than 500 msec, and in the judgment of the investigator(s) and sponsor is determined to be due to cause(s) other than investigational product, treatment may be continued with regular ECG monitoring. If in that timeframe the QTcF intervals rise above 500 msec the investigational product will be held until the QTcF interval decreases to 500 msec. Participants will then re-start the investigational product at the next lowest dose level. If the QTcF interval has still not decreased to 500 msec after 2-weeks, or if at any time a participant has a QTcF interval >515 msec or becomes symptomatic, the participant will be removed from the study. Additional triplicate ECGs may be performed as clinically indicated.

Prior to concluding that an episode of prolongation of the QTcF interval is due to investigational product, thorough consideration should be given to potential precipitating factors (eg, change in participant clinical condition, effect of concurrent medication, electrolyte disturbance) and possible evaluation by specialist.

If participant experiences a cardiac or neurologic AE (specifically syncope, dizziness, seizures, or stroke), an ECG (triplicate) should be obtained at the time of the event.

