**CCI**  
[REDACTED]  
[REDACTED]  
[REDACTED]  
[REDACTED]  
[REDACTED]

26. **Adverse Event (AE) Assessments:** Adverse events should be documented and recorded at each visit using the National Cancer Institute Common Terminology Criteria for Adverse Events (NCI CTC AE) version 4.03. Participants must be followed for AEs for 6 months after the last study treatment administration or until all drug related toxicities have resolved, whichever is later; or earlier than 6 months should the participant commence another anticancer therapy in the meantime. For serious adverse events (SAEs), the active reporting period to Pfizer or its designated representative begins from the time that the participant provides informed consent, which is obtained prior to the participant's participation in the study, ie, prior to undergoing any study-related procedure and/or receiving investigational product, through and including the 6 month follow-up period. Serious adverse events occurring after the active reporting period has ended should be reported to the sponsor if the investigator becomes aware of them; at a minimum, all serious adverse events that the investigator believes have at least a reasonable possibility of being related to investigational product are to be reported to the sponsor.
27. **Concomitant Treatments:** All concomitant medications and non-drug supportive interventions should be recorded in the CRF.
28. **End of Treatment Visit:** The End of treatment visit will be completed at the timepoint when a decision is made to discontinue study treatment. This can occur during Cycles 1 or 2 or during the Maintenance Treatment Phase of the study. Obtain these assessments if not completed in the past two weeks (past 6 weeks for tumor assessments).
29. **Follow up:** At least 28 days, and no more than 35 days after discontinuation of study treatment, participants will return to complete the required assessments. Participants will then return at Month 2, Month 4 and Month 6 to complete the required assessments.

**SCHEDULE OF ACTIVITIES FOR DOSE ESCALATION (Amendment 6); COHORTS 1A THROUGH 4A, COHORTS 6A THROUGH 9A AND DOSE EXPANSION COHORTS 1B THROUGH 3B AND 5B –**

The schedule of activities table provides an overview of the protocol visits and procedures. Refer to the **ASSESSMENTS** section of the protocol for detailed information on each assessment required for compliance with the protocol.

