### 3. STUDY DESIGN

#### 3.1. Study Overview

[figure not shown]
This is a Phase 1, open label, multi-center, multiple dose, safety, PK, CCI and immunogenicity study evaluating the components of a vaccine-based immunotherapy regimen for prostate cancer (PrCa VBIR). PrCa VBIR consists of the following components: Adenovirus (AdC68), pDNA and tremelimumab. In addition, cohorts will evaluate PrCa VBIR when given in combination with PF-06801591.

The study is divided in to two parts, Dose Escalation (Part A) followed by Dose Expansion (Part B). The overall design is presented in [Figure 1](#) below.

Participants will participate in the treatment period of the study for approximately 9 months. This includes a 28 day screening period followed by two cycles of treatment (each 4 months in duration for a total of 8 months). Participants will then enter the maintenance phase of the study where they will continue to receive their assigned components, at the frequencies outlined in the [schedule of activities](#). Treatment will continue until: disease progression, participant refusal or unacceptable toxicity occurs. Participants who demonstrate clinical benefit with manageable toxicity and who are willing to continue receiving study treatment will be given the opportunity to continue treatment upon agreement between the investigator and sponsor. When the participant discontinues treatment, they will then enter a 6 month post-dose follow-up period. The end of the study is the last participant last visit.

A cycle of the PrCa VBIR includes at minimum an AdC68 priming dose given intramuscularly (IM) on Day 1, followed by a total of three doses of DNA, given IM using an electroporation device at 4-week intervals for another 12 weeks (16 weeks total). Beginning with Cohort 3A, the PrCa VBIR cycle will also include tremelimumab given as SC injections at close proximity to the vaccinated muscles and the vaccine draining lymph nodes every four weeks at the immunization time points. For participants enrolled in Cohorts 6A through 9A or Cohorts 3B or 5B, the PrCa VBIR cycle will also include PF-06801591 given as SC injections at close proximity to the vaccinated muscles and the vaccine draining lymph nodes every four weeks at the immunization time points. After completing two cycles of treatment ( $\approx$ 8 months treatment duration), the participants will then enter the maintenance phase of the study.

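### Protocol 7.1.4 removes participants with marked QTcF prolongation from the study, while 3.1, 6.3 and Schedule footnotes 26 and 29 require 6 months of follow-up after treatment stops (low-severity wording conflict)

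*Protocol*

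**What the plan says.** Protocol Section 7.1.4 gives three triggers: QTcF not down to 500 msec after 2 weeks, QTcF above 515 msec at any time, or symptoms. All three lead to the same place: "or if at any time a participant has a QTcF interval >515 msec or becomes symptomatic, the participant will be removed from the study". The sentences just before it concern holding and restarting the investigational product, so only this sentence moves from the product to the study.

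The general rules on stopping treatment read differently:

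- Section 3.1: "When the participant discontinues treatment, they will then enter a 6 month post-dose follow-up period".
- Section 6.3: those who permanently stop study drug complete the End of Treatment visit "and then enter the follow-up period which includes 6 months of additional evaluations".
- Section 6.4: "Participant withdrawal may include either: (a) withdrawal from treatment with continued follow up, or (b) withdrawal from treatment and no further follow up".
- Section 6.4.1 lists, among reasons for stopping treatment, "Unacceptable toxicity, including treatment-related DLT". Section 6.4.2 opens its separate list with "Reasons for withdrawal from study follow-up may include" and names completion, sponsor termination, loss to follow-up, refusal and death.
- Part B Schedule of Activities, footnote 26: "Participants must be followed for AEs for 6 months after the last study treatment administration or until all drug related toxicities have resolved". The later of the two applies, with an earlier end only if another anticancer therapy begins.
- Footnote 28: "The End of treatment visit will be completed at the timepoint when a decision is made to discontinue study treatment". Footnote 29 then sets a visit at 28 to 35 days and visits at Months 2, 4 and 6.

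Sections 5.4.4.1 and 5.4.4.2 show the consistent form. A participant who would need too low a dose of AdC68 or tremelimumab stops treatment and goes into follow-up, unless the investigator and sponsor agree otherwise.

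**The concern.** Leaving treatment and leaving the study are separate acts in this protocol, and Section 6.4 is built on that separation. Section 7.1.4 prescribes the second act for an event that elsewhere leads to the first.

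Safety is the Part B primary objective, and Amendment 8 added troponin monitoring because of myocarditis risk. A site that took 7.1.4 at its word would end scheduled visits for participants with a marked ECG abnormality, who are the ones a safety study most needs to keep observing. Part B enrolment is closed, but Section 7.1.7 still sets dosing rules for participants who are ongoing, so the trigger can still occur.

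There is also a reporting consequence. SAP 8.1.2.1 presents two discontinuation counts, one for stopping study medication because of adverse events and one for leaving the study because of them. The wording of 7.1.4 would place a QTcF stop in the second.

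**Working it through.** No statistical calculation applies and the plan gives no figure to reproduce. The check compares the provisions and then counts what a literal reading could drop.

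**Which provisions conflict with 7.1.4**

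1. Sections 3.1 and 6.3 apply to anyone who stops treatment. A participant removed under 7.1.4 has stopped treatment, and neither section excepts QTcF cases. These conflict directly.
2. Footnotes 26 and 29 set the adverse event follow-up and the visits. The only early end in footnote 26 is a new anticancer therapy. These conflict directly.
3. Section 6.4 and its subsections give indirect support. Toxicity appears under withdrawal from treatment. Of the 5 listed reasons for leaving follow-up, 0 are toxicity or QTcF, but that list is not exhaustive.
4. Footnote 28 requires only the End of Treatment visit. It says nothing about 6 months.

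In the Amendment 6 schedule, which also covers the Part A cohorts, the same footnotes are numbered 25, 27 and 28.

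**Visits at risk per affected participant**

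- End of Treatment (1) + Months 1, 2, 4 and 6 (4) = 5 at most.
- If the final visit that Section 6.4.2 tells the investigator to request takes the place of End of Treatment: 5 − 1 = 4.
- Fewer if a new anticancer therapy starts.

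**Scheduled cardiac tests at risk (Schedule for Cohorts 3B and 5B)**

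The table is broken in the text available. I assume that its last five columns are End of Treatment and Months 1, 2, 4 and 6.

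- Triplicate ECG: End of Treatment and Month 1 = 2.
- ECHO or MUGA: End of Treatment = 1.
- Footnote 28 waives End of Treatment assessments done in the past two weeks. If that covers the ECG: 2 − 1 = 1. Since the trigger arises during ECG monitoring, this will often be the case.

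**What does not change**

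- Section 8.2 keeps SAE reporting open through the 6-month follow-up period.
- Footnote 26 counts adverse event follow-up from the last dose, not from the last visit.
- Section 7.1.4 itself permits further triplicate ECGs when clinically indicated.
- The triggering QTcF stays in the ECG analysis (Protocol 9.5.3, SAP 8.1.2.2).
- The safety analysis set depends only on receiving a dose (Protocol 9.1, SAP 5.1). The DLT definition in Section 3.2 is untouched.

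**The case against.** The strongest reply is that the protocol already deals with this. Anyone caught by 7.1.4 has permanently stopped study drug, and that alone sets off the follow-up rules, which are explicit and stated several times. Section 7.1.4 is a paragraph on ECG monitoring. It neither mentions follow-up nor waives it.

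The protocol's usage elsewhere points the same way. The text in Section 3.1 on treating for at least 24 weeks speaks of removing a participant when it means stopping treatment. Section 5.4.4.3 and the footnote to Table 6 tie staying in the study to continuing or resuming therapy. Most sites would probably carry out the follow-up anyway. Section 6.4 also recognises withdrawal without follow-up as a possible route.

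Most of this stands, and it is why the point is rated low. It does not remove the conflict. The sentence is a mandatory safety instruction, the protocol elsewhere separates the two kinds of withdrawal, and the correct form is available in Section 5.4.4.1.

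A reader might infer that SAE and adverse event data would be lost for these participants. The documents do not support that. SAE reporting continues under Section 8.2. That section does end CRF recording of adverse events at the last visit, but footnote 26 independently requires follow-up from the last dose. A reader might also take Section 6.4.1 and footnote 28 as requiring 6 months of follow-up themselves. They do not: the first lists reasons for stopping treatment, and the second sets one visit.

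**Conclusion.** The phrase in 7.1.4 is wrong as written, at low severity. It conflicts directly with Sections 3.1 and 6.3 and Schedule footnotes 26 and 29. Section 6.4 and its subsections lend indirect support.

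The size is at most 5 scheduled visits per affected participant, with up to 2 triplicate ECGs and 1 ECHO or MUGA, plus a possible misplacement in one descriptive count. The test counts rest on the assumed column order, and the whole loss depends on a site following the phrase literally.

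The number of participants affected is unknown. The documents give no frequency of QTcF above 515 msec, screening excludes QTc above 470 msec, and no further Part B participants will be enrolled. I therefore give no cohort percentage.

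It would go too far to infer that the primary safety analysis is compromised or that the sponsor meant to end follow-up for these participants. No estimate, DLT rule or analysis set depends on the phrase, and usage elsewhere suggests that only treatment was meant.

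**What to change.** In Section 7.1.4, change the consequence for all three triggers from leaving the study to: *will be permanently withdrawn from study treatment, complete the End of Treatment visit and enter the 6-month follow-up (Section 6.3)*.

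The cost is one phrase, in a clarification letter or at the next amendment. All the visits and tests are already in the Schedule, so none is added. The SAP needs no edit, because these stops would then fall under discontinuation of study medication in 8.1.2.1.
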